#### 4.8.3 PRO-CTCAE

The patient reported outcomes version of the common criteria for adverse events (PRO-CTCAE), a PRO version of the CTCAE system developed by the National Cancer Institute (NCI), is included to assess tolerability from the patient’s perspective. It was developed in recognition that collecting symptom data directly from patients can improve the accuracy and efficiency of symptomatic AE data collection. Symptoms have been converted to patient terms (e.g., CTCAE term “myalgia” converted to “aching muscles”). It characterizes the frequency, severity and interference of symptomatic treatment toxicities, such as pain, fatigue, nausea, and cutaneous side effects, reported from the subject’s perspective.

PRO-CTCAE data at baseline will be presented as the number (%) of subjects with each level of attribute item for each PRO-CTCAE symptom term. Change from baseline at all visits will be presented in 3 categories: improved, no change or worsened from baseline for each PRO-CTCAE symptom term. A bar chart of the incidence by visit will be presented for each symptom term.

#### 4.8.4 Sensitivity Analyses

Sensitivity analyses will be performed for all PRO endpoints by excluding subjects who had at least 1 missing visit due to COVID-19. Sensitivity analyses will be performed in the same manner as the primary PRO analyses.

#### 4.8.5 Exploratory Analyses

A mixed model repeated measures (MMRM) model may be developed to analyze the CFB of QoL over study visits through Cycle 6. Subjects in the ITT population having at least a baseline value and one value after randomization should be included in this analysis. The model may consider CFB as the dependent variable and include the following variables: treatment, visit, stratification factors, baseline value, interaction of visit and baseline, interaction of treatment and visit. Subject will be a random effect. Least square means and their 95% confidence intervals may be computed. Line graph presentation of least square mean plots of scores versus time point may be produced.

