		Cycle 1 c		Subsequent Cycles c		PTx Safety Follow-up 30 days after last dose of study drug e (± 3 d)	PTx Follow-up every 8 week f (± 7 d)
Study Day (visit window in days)	Day -35 to -1	Day 1 d	Day 15 d (± 2 d)	Day 1 d (±2 d)	(+14 d; within 14 d of last dose of study drug)		
Elacestrant group dd		{ ----- yOnce Daily					
SOC treatment group -aromatase inhibitor ee		{ ----- yOnce Daily					
SOC treatment group – fulvestrant ff		C1D1, C1D15, and Day 1 of every subsequent cycle					
Drug compliance gg		{----- y					
Adverse events hh		{----- y					

Sponsor:	Radius		
Protocol:	RAD1901-308		
Document Version No.:	1.1 (Final)	Document Date:	10-MAY-2021

Procedures/Assessments	Screening a	Active Treatment Period			End of Treatment (EOT) b	Post-Treatment (PTx)	
		Cycle 1 c		Subsequent Cycles c			
Study Day (visit window in days)	Day -35 to -1	Day 1 d	Day 15 d (± 2 d)	Day 1 d (±2 d)	(+14 d; within 14 d of last dose of study drug)	PTx Safety Follow-up 30 days after last dose of study drug e (± 3 d)	PTx Follow-up every 8 week f (± 7 d)
Prior/Concomitant medications/treatments ii	{----- y						
Survival follow-up for subjects who discontinue treatment f						X	

- a. All Screening assessments must be completed within 35 days prior to randomization (all imaging must be completed within 28 days prior to randomization unless otherwise specified). All surgical procedures related to breast cancer diagnosis must be recorded.
- b. If EOT falls on Day 1 of a cycle and the subject is withdrawing, the EOT assessments are to be completed instead of the Cycle Day 1 assessments. Assessments completed within the previous 14 days do not have to be repeated at the EOT visit.

Sponsor:	Radius		
Protocol:	RAD1901-308		
Document Version No.:	1.1 (Final)	Document Date:	10-MAY-2021

- 
- c. A Cycle is 28 days.
  - d. All assessments are to be performed pre-dose on scheduled visit days unless otherwise indicated. Procedures maybe performed  $\pm 2$  days relative to the visit.
  - e. Onsite visit preferred; if this is not feasible, telephone contact is acceptable. If follow-up assessments are conducted by telephone, the PROs are to be omitted.

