- k. PRO questionnaires are to be completed by the subject using the electronic tablet provided while in clinic (cannot be taken home) at the beginning of the study visit and prior to any other assessments or significant interactions with site staff. PRO questionnaires will be performed on C1D1, C1D15, C2D1, and D1 of each subsequent cycle through C4, then D1 of every other cycle thereafter starting with C6 (ie, C2, C3, C4, C6, C8, C10, etc), at EOT, and at the Safety Follow-Up visit (unless this visit is performed via phone contact). Note: If a certified translation for any PRO questionnaire is not available for a subject, that specific PRO assessment can be omitted, but the reason must be documented.
  - l. Physical examination at Screening to include total body examination of general appearance, skin, neck (including thyroid), ears, eyes, nose, throat, lungs, heart, abdomen, back, lymph nodes and extremities and a clinical neurological examination. Post-Screening physical examinations may be targeted based on findings present at Screening or subject complaints. Significant findings at Screening should be recorded as medical history or AEs as appropriate and clinically significant findings at subsequent visits should be recorded as AEs.
  - m. Vital signs (temperature, respiratory rate, sitting blood pressure, and sitting pulse rate) are to be performed prior to phlebotomy at Screening and at every visit. On C1D1 and C1D15, all vital signs are to be assessed pre-dose and blood pressure is to be performed 4 hours ( $\pm$  30 minutes) post-dose (all subjects) and prior to phlebotomy for PK assessment (subjects taking elacestrant). On Day 1 of every subsequent cycle, all vital signs are to be assessed pre-dose.
  - n. 12-lead ECG is to be performed in triplicate, 2 minutes apart, at all time points after the subject has been supine for at least 5 minutes using the Sponsor- provided ECG equipment. ECGs will be performed pre-dose and 4 hours ( $\pm$  30 minutes) post-dose on C1D1 and pre-dose and 4 hours ( $\pm$  30 minutes) post-dose on C1D15. ECG will be performed pre-dose on C2D1, and each subsequent cycle through cycle 4, then D1 of every other cycle thereafter starting with C6 (ie, C6, C8, C10, etc) and at EOT. See Table 19 of the protocol.
  - o. Not required in women who have undergone bilateral surgical oophorectomy.

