X If the larger p-value is  $< 0.025$ , statistical significance will be claimed only for the endpoint associated with the smaller p-value. An alpha of 0.0025 will be passed along to OS only in the population in which PFS is significant. To control for the 2 different times the OS analysis will be conducted, the alpha level of 0.0025 will be distributed across the 2 time points. An alpha level of 0.0001 will be allocated at the time of the primary PFS analysis and an alpha level of 0.0024 will be allocated at the time of the final OS analysis. This adjustment is according to a Haybittle-Peto rule.

X If the larger p-value is  $\geq 0.025$ , statistical significance will not be claimed. In this case, no alpha will be passed along to OS. No claim regarding OS will be made.

OS will be evaluated at 2 time points: (1) at the time of the primary analysis of PFS and (2) when approximately 50% of all subjects (ESR1-mut and ESR1-mut-nd) have died. At the time of this amendment, the study is fully enrolled (N=478). The second analysis of OS will take place when approximately 239 subjects have died. At the time of the PFS analysis, it is expected that approximately 96 subjects will have died.

Among all subjects (ESR1-mut and ESR1-mut-nd), the study will have 60% power to detect a hazard ratio of 0.75 at a 1-sided alpha level of 2.5%. Assuming a median OS of 25 months for the SOC treatment group, this hazard ratio represents a median OS of 33 months for the elacestrant treatment group. This calculation also accounts for 1 interim analysis at an information fraction of 0.4 with an alpha spending equal to 0.0001 at the interim analysis.

The study has enrolled 228 ESR1-mut subjects. Approximately 114 OS events are expected among the ESR1-mut subjects at the time of the second analysis of OS. With 114 OS events, the study will have 39% power to detect a hazard ratio of 0.73 at a 1-sided alpha level of 2.5%. Assuming a median OS of 28 months for the SOC treatment group, this treatment effect represents a median OS of 38 months for the elacestrant treatment group, an increase of approximately 10 months among the ESR1-mut subjects. This calculation also accounts for 1 interim analysis at an information fraction of 0.4 with an alpha spending equal to 0.0001 at the interim analysis.

Unless otherwise specified, analyses of all other efficacy endpoints will be performed at the 2-sided alpha level of 5% without adjusting the p-values for multiple comparisons.

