Summaries of absolute and change from baseline values of each EORTC QLQ-C30 scale/item and associated 95% CI will be reported by scheduled visit for each treatment group. Line graph presentation of least square mean plots of scores versus time point will be produced.

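### The optional quality-of-life MMRM models within-subject dependence by a random subject effect alone; fitted literally, its late-visit intervals are too narrow if spread grows or correlation decays over time

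*SAP*

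**What the plan says.** SAP 4.8.5 is permissive about the model itself: "A mixed model repeated measures (MMRM) model may be developed to analyze the CFB of QoL over study visits through Cycle 6". The suggested terms are "treatment, visit, stratification factors, baseline value, interaction of visit and baseline, interaction of treatment and visit", so the mean is free to differ by arm at every visit. Dependence between a subject's repeated scores is covered by one sentence, and that one is firm: "Subject will be a random effect". The section gives no residual covariance structure, fallback order, degrees-of-freedom method or robust variance. On output it says "Least square means and their 95% confidence intervals may be computed", and its plot of least-square means is optional too.

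The visits follow from SAP Table 1: "PRO questionnaires will be performed on C1D1, C1D15, C2D1, and D1 of each subsequent cycle through C4, then D1 of every other cycle thereafter", with "A Cycle is 28 days". Post-baseline visits through Cycle 6 are therefore C1D15, C2D1, C3D1, C4D1 and C6D1, on study days 15, 29, 57, 85 and 141.

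SAP 4.8.2, on the EORTC QLQ-C30, makes a firm promise: "Line graph presentation of least square mean plots of scores versus time point will be produced". It names no model for that plot.

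**The concern.** A random intercept with independent, equal-variance residuals is compound symmetry: one variance for every visit and one correlation for every pair. Here the gaps between visits run from 14 to 56 days, and many subjects will have stopped treatment before Cycle 6. If change scores spread out over time, one pooled variance is too small late and too large early. If correlation fades with time, the model also relies too heavily on early scores when it estimates late means for subjects who have dropped out.

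At stake are the error bars on the visit-wise least-square means, above all at Cycle 6, the last modelled visit.

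**Working it through.** The documents state no SD, correlation, precision or power for QoL, so there is no planned figure to reproduce. The check asks how far the model-based standard error departs from the true one under stated assumptions.

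**Inputs from the documents**
- Five post-baseline visits, days 15, 29, 57, 85 and 141 (SAP Table 1).
- Mean free by visit and arm (SAP 4.8.5).
- Expected time on elacestrant of about 4 months (Protocol 5.3.1). As a second anchor, median PFS of 5.3 months on standard of care in ESR1-mut subjects (SAP 4.1).

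**Assumptions**
- Exponential time on treatment. C6D1 is 140 days after Day 1, or 4.6 months. Retention is 2^(-4.6/4) = 0.45 on the first anchor and 2^(-4.6/5.3) = 0.55 on the second.
- Dropout completely at random and equal in the two arms.
- Correlation either exchangeable at 0.6, or serial at 0.85 per 28 days.
- SD at C6D1 divided by SD at C1D15 of 1.0, about 1.25 or 1.5.

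**Step 1: full follow-up, by hand.** With complete data the fitted variance is the average of the visit variances, so the ratio of model-based to true SE is

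ratio at visit j = sqrt(mean visit variance / variance at visit j).

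Take SD rising in equal steps by visit: 1, 1.125, 1.25, 1.375, 1.5. The variances are 1, 1.266, 1.563, 1.891 and 2.25, with mean 1.594.
- C6D1: sqrt(1.594/2.25) = 0.84, an SE 16% too small.
- C1D15: sqrt(1.594/1) = 1.26, an SE 26% too large.

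For growth to 1.25 the variances are 1, 1.129, 1.266, 1.410 and 1.563, with mean 1.273. The C6D1 ratio is sqrt(1.273/1.563) = 0.90.

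**Step 2: with dropout.** The random-intercept covariance M = aJ + bI is fitted by maximum likelihood to the assumed true covariance V, averaged over dropout patterns. With A the weighted sum of M^-1 and B the weighted sum of M^-1 V M^-1, the model-based variance is A^-1 and the true variance is A^-1 B A^-1. Ratios at C6D1, with 45% retained and SD rising linearly in days:

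| SD ratio, last/first | Exchangeable | Serial |
|---|---|---|
| 1.0 | 1.00 | 0.88 |
| 1.26 | 0.86 | 0.77 |
| 1.5 | 0.77 | 0.71 |

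The top left cell is compound symmetry, with no error. Constant SD with serial correlation gives 1 - 0.88 = 12%. The four cells with growing SD run from 1 - 0.86 = 14% to 1 - 0.71 = 29%.

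**Step 3: sensitivity.** The table below uses 42-55% retention, and SD rising either by visit or by day:

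| SD ratio, last/first | Exchangeable | Serial |
|---|---|---|
| 1.0 | 1.00 | 0.86-0.90 |
| 1.25 | 0.86-0.89 | 0.76-0.82 |
| 1.5 | 0.77-0.81 | 0.69-0.76 |

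At SD ratio 1.5 the C1D15 ratio is 1.15-1.26, with full follow-up included.

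**Step 4: coverage.** A nominal 95% interval with ratio r covers 2Φ(1.96r) - 1. For r = 0.86 that is 2Φ(1.69) - 1 = 0.91. For r = 0.71 it is 2Φ(1.39) - 1 = 0.84.

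**The case against.** The strongest reply is that the SAP is silent rather than wrong. A reader might infer that the random subject effect forces compound symmetry. The documents do not say so: nothing in 4.8.5 states that residuals are independent or share one variance, a structured residual could be added, and the name MMRM often denotes an unstructured covariance. That objection stands against the word forces. It does not remove the point. No residual structure is named, and a random intercept on top of a fully unstructured residual is redundant because its variance cannot be identified. The usual unstructured model therefore needs this sentence replaced.

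The size is also open to challenge. That change scores spread and decorrelate over time is an assumption here; no figure in either document supports it. Growth in spread alone gives less than growth combined with serial correlation: at SD ratio 1.25 with exchangeable correlation and 42-55% retention the narrowing is 11-14%.

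A reader might further infer an inflated false-positive rate for the QoL comparison. The documents do not support that either. The model is optional, and SAP 4.8 specifies no Cycle 6 between-arm contrast or p-value. Descriptive 95% intervals for change from baseline by visit are already committed in SAP 4.8.2 and Protocol 11.3.7, and they do not depend on this model.

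Finally, the least-square-mean plot in 4.8.2 names no model and shows scores, whereas 4.8.5 models change from baseline. It cannot be shown that the plot must come from this model. Even so, SAP 4.8 describes no other model that yields least-square means, so the mismatch between a firm promise and an optional source is real.

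**Conclusion.** The point holds as a gap with a better standard alternative. Followed as written, the model is a random intercept with one variance and equal correlation over days 15 to 141. The direction of the error is clear when that structure fails: late intervals too narrow and, where spread grows, the earliest too wide.

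The size is conditional. With about 45% retention and SD growth of about 1.25- to 1.5-fold, the Cycle 6 standard error is roughly 14-30% too small, and a nominal 95% interval covers about 84-91%. These figures rest on assumed SD growth, correlation and retention, and on dropout at random that is equal in both arms. No single percentage can be attributed to the plan.

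The priority is low. The effect is confined to exploratory patient-reported estimates.

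**What to change.** In SAP 4.8.5, replace the random-effect sentence with:

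> Within-subject covariance will be unstructured across visits (no random subject effect), with Kenward-Roger degrees of freedom; if it does not converge, heterogeneous Toeplitz, then heterogeneous AR(1).

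Reconcile SAP 4.8.2 with 4.8.5: either commit to the model or make the 4.8.2 least-square-mean plot conditional on it, and say whether the plot shows scores or change from baseline.

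The cost is one SAP sentence, one program statement and a wording alignment. Five visits need 5 × 6 / 2 = 15 covariance parameters, which is modest for 478 subjects and for the 228 ESR1-mut subjects (SAP 4.2.6). At 45% retention about 0.45 × 228 = 103 of the latter would still contribute at Cycle 6. The downside is that the fallback order is needed in case the unstructured model does not converge.

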### 4.9 Pharmacokinetic Evaluations

Elacestrant plasma concentrations will be summarized descriptively (with n, mean, standard deviation, CV, median, minimum, maximum, geometric mean and its associated CV) by visit and nominal

Sponsor:	Radius		
Protocol:	RAD1901-308		
Document Version No.:	1.1 (Final)	Document Date:	10-MAY-2021

timepoint (pre-dose or 4 hours post-dose) for ESR1-mut subjects, all subjects (ESR1-mut and ESR1-mut-nd) and ESR1-mut-nd subjects. Plot of geometric mean of the elacestrant concentrations by nominal time point will also be presented.

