4.3. Treatment Assignment

Subjects will be randomized in a 1:1 to ratio to one of the following treatment groups:

- Elacestrant 400 mg QD orally on a continuous dosing schedule
- SOC with one of the following options:
 - Fulvestrant 500 mg administered IM into the buttocks as two 5 mL injections on C1D1, C1D15 and C2D1 and Day 1 of every subsequent 28-day cycle
 - Anastrozole 1 mg QD orally on a continuous dosing schedule
 - Letrozole 2.5 mg QD orally on a continuous dosing schedule
 - Exemestane 25 mg QD orally on a continuous dosing schedule

Crossover from 1 treatment group or therapy to another will not be allowed while participating in the trial.

Subjects will be stratified by the following criteria:

- ESR1 mutational status detected by ctDNA (ESR1-mut vs ESR1-mut-nd)
- Prior treatment with fulvestrant (yes vs no)
- Presence of visceral metastases (yes vs no); visceral includes lung, liver, brain, pleural, and peritoneal involvement

The following contraindications must be adhered to:

- Known hypersensitivity to any of the SOC options or their excipients would preclude treatment with that particular therapy
- Therapeutic anticoagulation therapy or bleeding disorder that would, in the Investigator's opinion, preclude treatment with fulvestrant

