Dose interruptions of elacestrant of ≤ 14 consecutive days are permitted at any point during treatment. A dose interruption of >14 consecutive days requires discussion with RADIUS prior to continuation on study.

No dose escalations above the starting dose of 400 mg QD are permitted.

Table 8: Elacestrant Dose Reduction Guidelines

Dose Level	Elacestrant Dose
Starting dose	400 mg QD
-1 (1 st dose reduction)	300 mg QD (25% dose reduction) ^a
-2 (2 nd dose reduction)	200 mg QD (50% dose reduction) ^b

QD = once daily

^a Three 100 mg tablets

^b Two 100 mg tablets

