11.3.8. Pharmacokinetic Analysis

Elacestrant plasma concentrations will be summarized descriptively (with n, mean, standard deviation, coefficient of variation [CV], median, minimum, maximum, geometric mean and its associated CV) by visit and nominal time point (pre-dose or 4 hours post-dose; see [Table 18](#) and [Table 19](#) in Appendix 2) for ESR1-mut subjects and all subjects (ESR1-mut and ESR1-mut-nd). Plot of geometric mean of elacestrant plasma concentrations by nominal time point will also be presented.

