 - x. If bone lesions are identified at baseline (ie, during Screening), bone scans or whole body MRI are to be repeated during the active treatment phase (using the same modality used during Screening), every 24 weeks (± 7 days), and as clinically indicated, from the date of randomization, and at time of confirmation of CR. If no bone lesions are identified at baseline, bone scans or whole body MRI are to be repeated during active treatment phase only when clinically indicated and are required at time of confirmation of CR. At EOT, bone scans or whole body MRI are required for subjects with bone lesions identified at Screening, unless disease progression has been confirmed elsewhere or a scan has been performed within the last 12 weeks. See [Table 20](#).
 - y. Suspicious abnormalities (ie, hotspots) identified on bone scan or whole body MRI at baseline and on subsequent bone scans or whole body MRI MUST be confirmed. Diagnostic CT of chest and CT (with bone window settings) or MRI of abdomen and pelvis (or PET CT if CT images are of sufficient quality) are sufficient for evaluation of bone lesions involving the axial skeleton. Additional imaging of appendicular skeletal lesions (eg, skull, cervical spine, extremities) by bone window settings on CT scan or MRI are required if these sites are the only bone lesions to be followed. If a lesion is not confirmed to be metastatic by CT with bone windows or MRI, it should not be followed as a target or non-target lesion and it does not require re-assessment. The same modality must be used throughout the study for confirmation for a given lesion/subject. Areas that have received palliative radiotherapy should be followed as non-target lesions.
 - z. Blood samples for PK are to be collected at the following time points for subjects randomized to the elacestrant group only: C1D1 and C1D15: 0 h (pre-dose) and 4 h (± 30 min) post-dose; C2D1: 0 h (pre-dose). Investigators may obtain additional blood samples for PK analysis at the time(s) that significant AE or SAEs occur that are considered potentially related to the study drug. See [Table 19](#).

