Document Version No.:	1.1 (Final)	Document Date:	10-MAY-2021

---

IRC-assessed CBR will be analyzed using IRC-assessed CBE population. Local Investigator-assessed CBR will be analyzed using Local Investigator-assessed CBE population.

- x **Pharmacokinetic (PK) Population:** The PK population consists of all subjects who received at least 1 dose of elacestrant and have plasma elacestrant concentration data for at least 1 scheduled time point. PK analyses will be performed using the PK population.
- x **Biomarker Population:** The Biomarker population comprises all safety subjects for whom baseline and at least 1 post-baseline result are available for the biomarker of interest. The exploratory biomarker analysis will be performed using the Biomarker population.

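### Elacestrant concentrations at C1D15 and C2D1 are pooled whatever dose was taken, so reduced-dose samples and pre-dose samples drawn off drug enter the trough and 4-hour summaries

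*SAP*

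**What the plan says.** SAP section 4.9 is the whole plan for the PK results: "Elacestrant plasma concentrations will be summarized descriptively (with n, mean, standard deviation, CV, median, minimum, maximum, geometric mean and its associated CV) by visit". The only other grouping is by nominal sampling time and by set (ESR1-mut, all-subject and ESR1-mut-nd), and geometric means are plotted. Protocol section 11.3.8 groups the same way, "by visit and nominal time point (pre-dose or 4 hours post-dose", for the ESR1-mut and all-subject sets.

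The PK population in SAP section 3.1 is everyone who "received at least 1 dose of elacestrant and have plasma elacestrant concentration data for at least 1 scheduled time point". It sets no condition on the dose taken or on recent dosing.

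Every elacestrant subject starts on the same regimen, "Elacestrant 400 mg QD orally on a continuous dosing schedule" (protocol section 4.3). Protocol Table 8 then allows steps down to 300 and 200 mg. Interruptions of up to 14 "consecutive days are permitted at any point during treatment" (protocol section 4.5.1), and longer ones are possible after discussion with the sponsor.

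Sampling is pre-dose and at 4 h on C1D1 and C1D15, and pre-dose only on C2D1 (protocol Appendix 2, Table 18 notes). Protocol section 3.2.2 and SAP section 2.5.2 label the pre-dose samples on C1D15 and C2D1 as trough concentrations.

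**The concern.** A trough is the level just before the next dose under regular dosing. A sample taken several days after the last dose is not one, yet the plan averages it into the trough summary. A level measured on 200 or 300 mg is likewise averaged with levels on 400 mg, and the table does not show the mix.

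Each such sample lowers the summary. The affected samples are not a random subset either, because reductions, and often interruptions, follow toxicity (protocol Table 7).

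These tables also carry the PK objective alone. SAP section 6 says noncompartmental analysis is not possible with the time points collected, and that concentrations will be summarised instead. Because 400 mg once daily is the only assigned elacestrant dose, readers will tend to take the reported trough as the 400 mg trough.

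**Working it through.** The plan gives no PK figure to reproduce, so the check has two parts: which summaries can be affected, and by how much.

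**Which summaries**

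| Scheduled sample | Reduced dose | Interruption |
|---|---|---|
| C1D1 pre-dose | no, before any drug | no |
| C1D1 4 h | no, first 400 mg dose | no |
| C1D15 pre-dose | yes | yes |
| C1D15 4 h | yes | no, no dose that day |
| C2D1 pre-dose | yes | yes |

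A subject who has just restarted may also have a low 4 h level on C1D15, because the drug has not yet built up again.

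**Formulas**

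Let f be the share of samples affected and r their concentration relative to uninterrupted 400 mg dosing.

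- Pooled geometric mean ratio = r^f
- Pooled arithmetic mean ratio = 1 - f(1 - r)
- Trough after d missed days: r = 2^(-24d / half-life)
- Reduced dose: r = 300/400 = 0.75 or 200/400 = 0.50. This assumes dose-proportional exposure; protocol section 2.2.2.1 says only that exposure is dose-dependent.

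**Inputs**

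- Half-life 30 to 50 h (protocol section 2.2.2.1).
- TEAE leading to interruption, tablets: 8/24 = 33.3% (protocol Table 5), at any time on treatment.
- Median treatment 3.8 months (protocol section 5.3.1), about 116 days.
- Related Grade 3 or 4 TEAE: 1/24 = 4.2% on tablets and 10/66 = 15.2% overall (protocol Table 5). This stands in for the share reduced, because Table 7 guidance lowers the dose only after such an event resolves.

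**Interruptions**

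Assume one interruption per affected subject, spread evenly over treatment. The share off drug on a given day is f = 0.333 x length / 116, and on average a subject is halfway through. Log concentration falls linearly with time, so the midpoint gives the correct average for the geometric mean.

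| Length | f | Mean days off | r (30 h; 50 h) | r^f (30 h; 50 h) | Geometric mean low by |
|---|---|---|---|---|---|
| 7 days | 2.0% | 3.5 | 0.144; 0.312 | 0.962; 0.977 | about 2-4% |
| 14 days | 4.0% | 7 | 0.021; 0.097 | 0.855; 0.911 | about 9-14% |

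The arithmetic mean cannot fall by more than f, so by at most 2.0% or 4.0%. The geometric mean, which the plan also plots, is much more sensitive to a few very low values. The calculation leaves out the days of re-accumulation after a restart.

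**Reductions**

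- f = 4.2%: 0.75^0.042 = 0.988 and 0.50^0.042 = 0.972, so about 1-3% low.
- f = 15.2%, all at 200 mg: 0.50^0.152 = 0.900, so 10% low. This is an upper case.

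**The case against.** The strongest defence is that the plan promises nothing more. The objective is to assess the PK of elacestrant, and no section calls the summary an estimate of 400 mg exposure. Levels observed under the regimen as actually taken are real data, and an all-treated summary of them is legitimate. No test, threshold or decision in the documents rests on the table; protocol section 2.4 bases the 400 mg choice on earlier studies. The median, minimum and maximum are reported too, and a few low troughs barely move a median. SAP sections 4.12.1 and 4.12.1.1 provide listings of exposure and of missed doses, so affected samples could be traced.

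Most of this stands, and it is why the pooled table should stay. It does not justify putting an off-drug value under a trough label, and listings do not correct a summary table.

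A reader might also infer a large bias from the 31.8% of subjects in the earlier studies who had a TEAE leading to interruption. That figure counts interruption at any time, not on a sampling day. A share of 5% or 10% off drug on one visit day has no support in the documents. Nor has 20% of subjects on 200 mg: under Table 7 that takes a related Grade 3 or 4 event, its resolution, a recurrence and a second resolution, here by about Day 29 at the latest.

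**Conclusion.** The point holds for three of the five scheduled summaries: C1D15 pre-dose, C1D15 4 h and C2D1 pre-dose. As written, the plan averages reduced-dose samples into all three and off-drug samples into the two trough summaries, and both effects lower the results.

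The likely size is modest but can be material: about 2-4% (7-day interruptions) to 9-14% (14-day interruptions) off the geometric mean trough, plus about 1-3% from reductions. These figures rest on evenly spread interruptions, Phase 1 tablet rates carried over to this trial, a 4.2% share reduced and dose-proportional exposure. Interruptions that cluster early or last longer would raise them. The documents do not give the number of subjects affected at either visit.

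A reader might conclude that the trial's estimate of 400 mg exposure is biased low. The documents define no such estimate, so that holds only if the pooled table is read as one. A reader might also think that interruptions distort the 4-hour levels. A subject who takes no dose that day has no true 4-hour post-dose level. The primary and key secondary analyses are untouched.

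**What to change.** In SAP section 4.9, for C1D15 and C2D1:

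- Add a summary by visit, nominal time and actual dose level at sampling.
- Flag pre-dose samples not preceded by uninterrupted dosing over the protocol's time to steady state (about 6 days, protocol section 2.2.2.1), and exclude them from the trough summary by dose level.
- Report this beside the all-treated pooled table, and keep the ESR1-mut and all-subject sets that the protocol requires.

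The cost is SAP wording and programming. SAP section 4.12.1.1 already records each uninterrupted same-dose period and opens a new one at a dose change or missed dose, so no new data are needed.

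There are two downsides. The by-dose summary has slightly fewer samples. The uninterrupted 400 mg group also favours subjects who tolerate the drug; if toxicity rises with exposure, that group may lose high-exposure subjects. A note with the table should say so. For the same reason the uninterrupted 400 mg group should not replace the pooled table as the only main result.
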